3.3 SELECTION OF TRIAL POPULATION

A sufficient number of patients will be screened to ensure that an adequate number of patients will be randomized.

A total of 350 patients in approximately 45 sites, 13 countries will be randomised. More sites may be initiated depending on recruitment rate. To ensure sufficient enrolment of men, recruitment of women will be capped at 70 % and the randomisation will be stratified according to sex.

Screening of patients for this trial is generally competitive, i.e. screening for the trial will stop at all sites at the same time once a sufficient number of patients has been screened. The sponsor may require some site or country to stop recruitment in case they dominate the recruitment in a way that might cause variety or quality issues. Investigators will be notified about screening completion and will then not be allowed to screen additional patients for this trial.

A log of all patients enrolled into the trial (i.e. who have signed informed consent) will be maintained in the Investigator Site File (ISF) irrespective of whether they have been treated with investigational drug or not.

If a patient is enrolled in error (does not meet all inclusion criteria or meets one or more exclusion criteria on the day of enrolment), the sponsor should be contacted immediately.

Re-screening is not allowed. Re-testing (of assessments) should be discussed with Clinical Trial Manager (CTM).

Re-testing:

If the investigator believes that an ineligible lab test result is the result of an error or extenuating circumstance, then that lab test can be retested once without the patient having to be re-screened. The retest should be carried out as soon as possible so the laboratory test results will be received within the next planned visit windows in order to avoid protocol window violations.

Patients must have had a stable weight for 3 months before entering the trial. If this criterion cannot be documented, it is possible to extend the screening period up to 12 weeks to allow checking the weight stability. Documentation upon patients' interview is acceptable.

3.3.1 Main diagnosis for trial entry

The main diagnosis for patients to enter the trial is BMI ≥ 27 kg/m² without diabetes at screening.

Please refer to [section 8.3.1](#) (Source Documents) for the documentation requirements pertaining to the in- and exclusion criteria.

3.3.2 Inclusion criteria

1. Adult ≥ 18 years and < 75 years of age at screening
2. Signed and dated written informed consent in accordance with ICH-GCP and local legislation prior to admission to the trial.
3. Obesity or Overweight defined as BMI ≥ 27 kg/m² at screening
4. A minimum absolute body weight of 70 kg for females and 80 kg for males at screening
5. Male or female participants. Women of childbearing potential (WOCBP)¹ must be willing and able to use two forms of effective contraception where at least one form is highly effective methods of birth control per ICH M3 (R2) that result in a low failure rate of less than 1% per year when used consistently and correctly. A list of contraception methods meeting these criteria is provided in the patient information. See section [4.2.2.2](#).
6. Patients must have undergone at least one previous unsuccessful nonsurgical weight-loss attempt per investigator's judgement

3.3.3 Exclusion criteria

1. Body weight change of over +/- 5% or more in the past 12 weeks prior to randomization. There must be documentation of weight in the past 12 weeks before randomization.
2. Obesity induced by an endocrinologic disorder (i.e. Cushing Syndrome, hypogonadism, growth hormone deficiency. However, well controlled hypothyroidism, polycystic ovarian disease are still allowed)
3. A HbA1c $\geq 6.5\%$ at screening or diagnosed with type 1 or type 2 diabetes mellitus
4. Exposure to GLP-1Ra based therapies within three months prior to screening
5. Any suicidal behaviour in the past 2 years, any suicidal ideation of type 4 or 5 in the C-SSRS within 3 months before screening, or during screening period
6. History of major depressive disorder within 2 years before randomization
7. Major depressive symptoms (defined as a screening Patient Health Questionnaire-9 [PHQ-9] score ≥ 15) at screening and/or during screening period
8. Diseases of the central nervous system (including but not limited to any kind of seizures or stroke), and other relevant neurological or psychiatric disorders at screening
9. Screening calcitonin ≥ 20 pg/mL ($\geq 5,84$ pmol/L)
10. Personal or family history of medullary thyroid carcinoma or multiple endocrine neoplasia syndrome type 2, manifest hypo- or hyperthyroidism at screening

¹ A woman is considered of childbearing potential (WOCBP), i.e. fertile, following menarche and until becoming postmenopausal unless permanently sterile.

A postmenopausal state is defined as no menses for 12 months without an alternative medical cause.

Permanent sterilisation methods include hysterectomy, bilateral salpingectomy and bilateral oophorectomy.

Please note that tubal ligation is NOT accepted as a method of permanent sterilisation and therefore a woman who underwent tubal ligation is still considered as WOCBP. However tubal ligation is considered as a method of highly effective birth control.

11. History of chronic or acute pancreatitis or elevation of serum lipase/amylase > 2x ULN, or fasting serum triglyceride levels of > 500 mg/dL (>5,65 mmol/L) at screening
12. Treatment with medication that potentially induce a change in body weight (e.g., steroids, antipsychotics), or anti-obesity medication including over-the-counter [OTC] medications, or participating in an organized weight loss program (e.g. ██████████[®] or ██████████[®]) within 3 months before screening
13. Prior surgery of the GI tract that could interfere with body weight (including minimally invasive/endoscopic bariatric devices, bariatric surgery including metabolic operation that involves resection and/or reconstruction of any portion of the gastrointestinal tract) except appendectomy and simple hernia repair before randomization. However, a patient previously treated with reversible weight loss devices such as gastric banding, or intragastric balloon and removed longer than 12 months before screening should not be excluded.
14. Resting Heart Rate >100 bpm at screening or randomisation
15. Systolic blood pressure ≥ 160 mmHg and/or diastolic blood pressure ≥ 95 mmHg at screening.
16. History or currently diagnosed with congestive heart failure, New York Health Association (NYHA) class III-IV at screening
17. A marked prolongation of QT/QTc (Fridericia) interval that is greater than 450 ms at screening or at the randomisation or any other abnormal clinically significant ECG finding at screening (e.g., type 2 second-degree AV block (Type Mobitz II) or third-degree AV block) – see [section 5.2.4](#).
18. Heart rhythm disturbances (e.g., bradycardia with baseline HR < 50 bpm, in the absence of medications that lower the heart rate), supraventricular tachycardia or tachyarrhythmia (e.g., atrial fibrillation, atrial flutter or ventricular tachycardia), considered by the investigator indicative of relevant cardiac disease or with abnormalities that may interfere with the interpretation of changes in ECG intervals at screening. Family history of long QT Syndrome, use of prescription or over-the-counter medications known to significantly prolong the QT or QTc interval at screening.
19. Treatment with medications known to cause heart block or bradycardia, such as beta-blockers, verapamil and diltiazem, unless these drugs are indicated for heart rate control or hypertension treatment
20. Any of the following conditions or procedures within the last six months prior to screening: myocardial infarction, unstable angina (e.g. CCS grading of Angina pectoris grade III and IV), arterial bypass graft (e.g. coronary bypass, carotid bypass, peripheral vascular disease bypass), percutaneous coronary intervention (diagnostic angiograms are permitted), transient ischaemic attack (TIA), cerebrovascular accident (stroke)
21. Women who are pregnant, nursing, or who plan to become pregnant while in the trial
22. A history of atopy (severe or multiple allergic manifestations) or clinically significant multiple or severe drug allergies, or intolerance to topical corticosteroids, or severe post treatment hypersensitivity reactions (including, but not limited to, erythema multiforme)

major, linear immunoglobulin A dermatosis, toxic epidermal necrolysis, anaphylaxis, angioedema, or exfoliative dermatitis)

23. Chronic or relevant acute infections (including but not limited to respiratory tract infections, urinary tract infection, bladder infection, enterocolitis, abscess, tuberculosis, meningitis, influenza, Epstein-Barr virus, HIV/AIDS, and hepatitis B or C, and SARS-CoV-2(as confirmed by PCR test, see [section 5.2.3](#))), within 2 weeks from screening or during screening.
24. Any condition which might jeopardize patient's safety or compliance with the protocol as judged by the investigator
25. Any documented active or suspected malignancy or history of malignancy within 5 years prior to screening, except appropriately treated basal or squamous cell carcinoma of the skin
26. Participation in another clinical trial within 90 days before screening

3.3.4 Withdrawal of patients from treatment or assessments

Patients may discontinue trial treatment or withdraw consent to trial participation as a whole ("withdrawal of consent") with very different implications; please see [sections 3.3.4.1](#) and [3.3.4.2](#) below.

Every effort should be made to keep the patients in the trial: if possible on treatment, or at least to collect important trial data.

Measures to control the withdrawal rate include careful patient selection, appropriate explanation of the trial requirements and procedures prior to trial enrolment, as well as the explanation of the consequences of withdrawal.

Patients should be made aware of potential anticipated GI side effects and investigators should provide guidance on how to avoid or overcome them.

The decision to discontinue trial treatment or withdraw consent to trial participation and the reason must be documented in the patient files and CRF. If applicable, consider the requirements for Adverse Event collection reporting (please see [sections 5.2.6.2.1](#) and [5.2.6.2](#)).

3.3.4.1 Discontinuation of trial treatment

An individual patient will discontinue trial treatment if:

- The patient wants to discontinue trial treatment, without the need to justify the decision.
- The patient has repeatedly shown to be non-compliant with important trial procedures and, in the opinion of both, the investigator and sponsor representative, is not willing or able to adhere to the trial requirements in the future.
- The patient cannot tolerate the drug despite all efforts taken
- The patient requires hospitalization due to drug related gastrointestinal adverse event assessed by investigator
- The patient needs to take concomitant medication that interferes with the investigational medicinal product or other trial treatment. Refer to [section 4.2.2.1](#)

- The patient can no longer receive trial treatment for medical reasons (such as surgery, adverse events, other diseases, or pregnancy).
- Sustained symptomatic hypotension or hypertension: For hypotension, episode of symptoms (such as light-headedness or dizziness) associated with a systolic blood pressure <100 mmHg for > 60 minutes or for hypertension, episode of symptoms such as headaches, shortness of breath or nosebleeds associated with a systolic blood pressure > 160 mmHg in at least three consecutive measurements, each at least 30 minutes apart.
- Clinically relevant changes in ECG (QT prolongation >500 ms or an increase of 60 ms versus baseline, or Type Mobitz II, or third-degree AV block), or any symptomatic AV block, newly developed atrial fibrillation, or atrial flutter that require medical intervention.
- Sinus tachycardia (HR >120/min in two consecutive assessments 5 minutes apart) and/or tachyarrhythmia (HR >110/min) or cardiac conditions requiring medical intervention.
- Ventricular tachycardia in ECG or syncope.
- Clinically relevant coronary artery disease (e.g. CCS grading of Angina pectoris grade III and IV or congestive heart failure, NYHA class III-IV).
- The patient shows an elevation of AST and/or ALT ≥ 3 -fold ULN combined with an elevation of total bilirubin ≥ 2 -fold ULN (measured in the same blood sample) and/or needs to be followed up according to the 'DILI checklist' provided in the ISF.
- The patient experiences an infection with Sars-CoV-2 (as confirmed by PCR test, see [Section 5.2.3](#)) and presents with signs or symptoms requiring discontinuation of treatment as per investigator's discretion.
- Patients newly diagnosed T2DM requires anti-diabetic treatments other than metformin
- Patients newly diagnosed acute pancreatitis
- Patients newly diagnosed medullary thyroid carcinoma
- Surgical treatment for obesity
- The patient develops suicidal ideation of type 4 or 5 in the C-SSRS (i.e. active suicidal thought with intent but without specific plan, or active suicidal thought with plan and intent). The patient should immediately be referred to a mental health professional for further work-up.
- Inadequate psychotherapy and/or pharmacotherapeutic treatment of a subject's psychiatric disorder
- The subject refuses mental health professional referral and, in investigator's opinion, it is unsafe for the subject to continue
- Treatment with orlistat, zonisamide, topiramate, lorcaserin, phentermine, bupropion, naltrexone, GLP-1 RAs alone or in combination prescribed for weight loss or any medication that could provide weight change in the opinion of the investigator
- Out of compliance with study drug (missing doses). Refer to missing dose [section 4.1.4](#)

Given the patient's agreement, a patient who discontinue drug should stay in the trial and follow procedures and visits as described in [section 6.2.2](#) except patients taking GLP-1 RA who should be withdrawn from trial.

For all patients the reason for withdrawal from trial treatment (e.g. adverse events) must be recorded in the CRF. These data will be included in the trial database and reported.

Pregnancy

If a patient becomes pregnant during the trial, the trial medication will be stopped, the patient will be followed up during the trial and until birth or termination of the pregnancy (see further details in [section 5.2.6.2.3](#)). The patient will be expected to attend the regularly scheduled study visits as outlined above.

There is no evidence of risk for partners of male participants, thus no need for male contraception.

Malignancies

In case of occurrence of malignant neoplasm, the Investigator should discontinue treatment with the trial medication, and notify the Sponsor. Diagnostics and treatment should be initiated according to local standard of care.

Suicidality

In case of signals of suicidal ideation or behaviour, the Investigator should discontinue treatment with the trial medication, notify the Sponsor and the patient should be referred to an appropriate psychiatric clinic.

If new efficacy/safety information becomes available, Boehringer Ingelheim will review the benefit-risk-assessment and, if needed, pause or discontinue the trial treatment for all patients or take any other appropriate action to guarantee the safety of the trial patients.

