6.2.3 Follow-up period and trial completion

A follow up visit has to be organized after a minimum of 4 weeks after last drug injection as outlined in the [Flow Chart](#) (FC).

Procedures to be completed at the follow-up visit can be found in the Flow Chart. The sequence of visit procedures will be the same as in the treatment period.

If a patient had withdrawn drug prematurely, he should also come for that follow-up visit. In addition, the patient will be asked to return to clinic every 4 weeks to measure body weight until the end of the planned treatment period, i.e. week 46. All efforts should be made at least to conduct the week 46 visit for all patients.

However, if this is not possible, a phone contact should be made at week 46 to obtain vital status and body weight measured at home on the study scale.

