PoCC will be established if at least one model is statistically significant, rejecting the null hypothesis of a flat dose response relationship for percentage change in body weight jointly over the candidate dose response models, with a contrast test controlled for the family-wise type I error rate at one sided $\alpha = 2.5\%$.

If PoCC is established, the statistically significant (best fitting) model(s) from the above candidate set will be refitted to the data to generate new estimates for all model parameters from the data. The target dose(s) will be estimated from the best fitting model(s) by incorporating information on the minimum clinically relevant effect and accounting for safety.

The primary analysis of percentage change from baseline in body weight at Week 46 will be performed using the FAS and will assign patients to the randomised maintenance dose. It will include all available data without regard to whether patients started the maintenance period

with a lower dose than the one randomised to. For patients who discontinued treatment early, a distinction will be made according to whether this is due to a COVID-19 pandemic-related reason or not. Patients who discontinued treatment early due to a pandemic-related reason (e.g. direct COVID-19 infection, drug supply issue, site closure, quarantine preventing site access) will have data handled after discontinuation as if they were missing. Patients who discontinued treatment early for any other reason will have all available data included after discontinuation, irrespective of whether such patients subsequently received any permitted anti-obesity treatments.

The above approach to the primary analysis specifies a hypothetical strategy for the intercurrent event of pandemic-related early treatment discontinuation, and a treatment policy strategy for the intercurrent event of non-pandemic-related early treatment discontinuation.

The primary endpoint will be summarised descriptively overall, and by pre-specified subgroups (to be specified in the TSAP, but which may include e.g. subgroups based on gender, baseline BMI and age at screening).

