5. ENDPOINT(S)

5.1 PRIMARY ENDPOINT(S)

The primary endpoint is the percentage change in body weight from baseline at Week 46.

Further details on the definition of baseline are given in [Section 6.7](#).

The primary endpoint is defined using body weight measured at the clinic, as recorded on the eCRF. Home-measured body weight recorded on the eDiary will not be used in the primary endpoint definition or in any analyses of the primary endpoint. All body weight data recorded on the eCRF will be considered eligible for primary endpoint purposes; specifically, no attempts will be made to identify and exclude any home measurement which may have been entered on the eCRF as a substitute for clinic measurement (if such identification is even possible).

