Prior to applying the visit windows specified below, it will first be determined whether the data record is on-treatment, as defined in [Section 6.1.6](#), for summaries or analysis which require this approach.

Unscheduled and repeat assessments (where relevant/available) are eligible for inclusion in visit windows.

For all variables except 12-lead ECG, if a patient has more than one non-missing value within the same visit window, the value closest to the target day will be selected. If two non-missing values are the same distance from the target day, the earlier of the two values will be selected.

For 12-lead ECG (only), scheduled visits take precedence over unscheduled visits. Once this rule has been applied, the measurement closest to the target day will be used. If there are two observations which have the same difference in days to the planned day (but are not on the same day), the later of the two values will be selected.

Derivation of last, minimum and maximum values where relevant in safety analyses will consider all available values, regardless of whether they were selected in the visit window.

The derivation of the maximum value of an ECG interval (or worst case of the morphological assessment, if applicable) will consider all on-treatment values (whether or not selected in any time window; see [Section 6.1.6](#) for definition of on-treatment).

Two different situations are envisaged, which are described in the following tables:

- Visit windows for variables scheduled to be assessed at all or many visits
- Visit windows for variables with a sparse visit schedule.

Table 6.7: 1 Visit windows for variables scheduled to be assessed at all or many visits

Period	Time Point	Target Day	Visit Window
Dose escalation	Week 2	15	2-21
	Week 4	29	22-35
	Week 6	43	36-49
	Week 8	57	50-63
	Week 10	71	64-77
	Week 12	85	78-91
	Week 14	99	92-105
	Week 16	113	106-119
	Week 18	127	120-133
Maintenance	Week 20	141	134-154
	Week 24	169	155-182
	Week 28	197	183-210
	Week 32	225	211-238
	Week 36	253	239-266
	Week 40	281	267-301
	Week 46	323	≥ 302

The relevant variables are expected to include body weight measured at the clinic and BMI derived from this, vital signs, routine non-fasting laboratory safety variables, 12-lead ECG and the mental health questionnaires (C-SSRS, PHQ-9).

These visits windows will also be used for waist circumference, although this is not scheduled to be captured at all weeks displayed.

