7.4 PRIMARY ENDPOINT(S)

Descriptive summaries of body weight and percentage change from baseline will be presented over time. These summaries will be produced in each of the following different ways:

- FAS, planned maintenance treatment, all data (i.e. both on-treatment and off-treatment as defined in [Section 6.1.6](#), and irrespective of any anti-obesity medications subsequently introduced for patients who discontinued treatment early)
- FAS, planned maintenance treatment, all data (as above) but censored for any early treatment discontinuation related to the COVID-19 pandemic (either direct COVID-19 infection or other indirect pandemic-related reason)
- FAS, planned maintenance treatment, on-treatment data only
- FAS, actual maintenance treatment, all data censored for COVID-19 related treatment discontinuation
- FAS, actual maintenance treatment, on-treatment data only.

The first descriptive summary above, which uses all available body weight data, will be repeated split at each time point according to whether the contributing data are on- or off-treatment.

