7.4.1 Primary analysis of the primary endpoint(s)

The primary analysis of the primary endpoint will be performed on the FAS, using planned maintenance treatment, and including all data censored for COVID-19 related early treatment discontinuation. This specifies a hypothetical estimand strategy for the intercurrent event of pandemic-related early treatment discontinuation, and a treatment policy strategy for the intercurrent event of non-pandemic-related early treatment discontinuation.

A COVID-19 related early treatment discontinuation is defined as either of the following situations):

- Direct patient COVID-19 infection: Reason for early treatment discontinuation is given on the End of Treatment eCRF page as “Adverse Event” and a treatment-emergent AE of “COVID-19” is recorded.
- Other COVID-19 restriction (site access, drug supply, quarantine, etc) which meant that study treatment could not be continued: Reason for early treatment discontinuation is given on the End of Treatment eCRF page as “Other” and the supporting comments indicate clearly “COVID-19”.

Further, “censored for” COVID-19 related treatment discontinuation is clarified to mean in practice that for patients who had a COVID-19 related treatment discontinuation (and only for these patients), only the on-treatment data will be used, as defined in [Section 6.1.6](#).

Missing data will be modelled based on what was observed up to the occurrence of these intercurrent events using direct likelihood approaches, which is a valid approach under the assumption that data are MAR.

An MMRM will be fitted to the percentage change in body weight values at each scheduled week (calculated as per [Section 6.7](#)) for this purpose. The MMRM will include fixed effects for baseline body weight as a continuous linear covariate, and treatment, gender, visit, treatment by visit interaction and baseline by visit interaction as factors. The Kenward-Roger approximation will be used to estimate the denominator degrees of freedom.

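### Weights measured during pregnancy enter the primary endpoint under the treatment-policy rule; the expected effect is small, but the estimand should name pregnancy separately

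*Protocol*

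**What the plan says.** **Follow-up.** Under Protocol 3.3.4.1 a patient who becomes pregnant stops trial medication but remains in the trial: "The patient will be expected to attend the regularly scheduled study visits as outlined above". For anyone who stops drug early, Protocol 6.2.3 adds a weighing schedule that runs to Week 46: "the patient will be asked to return to clinic every 4 weeks to measure body weight until the end of the planned treatment period".

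**Primary analysis.** Protocol 7.2.2 separates pandemic-related stops from the rest: "Patients who discontinued treatment early for any other reason will have all available data included after discontinuation". SAP 7.4.1 repeats this as "a treatment policy strategy for the intercurrent event of non-pandemic-related early treatment discontinuation". The only censoring is for COVID-19 related stops; for those patients ("and only for these patients), only the on-treatment data will be used").

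**Which weights count.** SAP 5.1 states: "All body weight data recorded on the eCRF will be considered eligible for primary endpoint purposes". SAP 6.7 gives Week 46 a window from day 302 onward with target day 323, and "if a patient has more than one non-missing value within the same visit window, the value closest to the target day will be selected". SAP 6.2 says that protocol deviations exclude nobody from an analysis set.

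**Other endpoints.** SAP 7.5.2 applies the primary data rule to the responder analyses. The continuous secondary endpoints, including weight change in kg, use on-treatment data only, which SAP 6.1.6 ends 28 days after the last dose. SAP 7.4 also plans a descriptive summary on "FAS, planned maintenance treatment, on-treatment data only".

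**The concern.** A treatment-policy strategy suits a patient who stops for tolerability or later takes another obesity drug, because her weight still measures the outcome of interest. In pregnancy the scale also records gestational gain, which says nothing about obesity response under any dose.

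The plan already gives one kind of stop its own strategy. Pregnancy is just as foreseeable: the protocol has testing, contraception and reporting rules for it. Yet the visible estimand text does not mention it, so these weights become the outcome of the randomised arm.

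The direction depends on the arm. In an active arm the apparent effect shrinks. In the placebo arm every dose-placebo difference grows. The Week 46 arm means feed MCPMod and the target-dose rule in SAP 7.4.1 (9% more reduction than placebo), which lies only 1 point from the assumed top-dose effect of -10%.

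SAP 6.6 leaves treatment-policy sensitivity analyses that depart from standard MMRM to be done post hoc. Without a rule set beforehand, how to treat a pregnant patient could be decided once her arm is known.

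**Working it through.** **Inputs from the documents.** 70 patients per arm, SD 7.0, placebo 0, top dose -10.0, and success defined by three criteria (Protocol 7.5); 350 randomised with women capped at 70% (Protocol 3.3); a contraceptive failure rate below 1% per year with consistent and correct use (Protocol 3.3.2); 46 weeks of treatment.

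**Assumptions not in the documents.** A displacement g of 10 to 20 percentage points in Week 46 weight for a pregnant patient. All women are treated as of childbearing potential, which overstates the number at risk.

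**Step 1: reproduce the plan's figures.** Contrasts built from the five stated shapes match SAP Table 7.4.1: 1 to three decimals. The one-sided 2.5% critical value is about 2.24. Success was simulated with 10,000 runs per shape, taking the lowest-AIC model among the significant shapes. At -10.0:

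| | Linear | Exponential | Emax1 | Emax2 | SigEmax | Average |
|---|---|---|---|---|---|---|
| Protocol Table 7.5: 1 | 82.8 | 83.3 | 83.8 | 83.3 | 89.0 | 84.4 |
| Recomputed | 82.2 | 82.2 | 83.7 | 83.0 | 90.2 | 84.3 |

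**Step 2: expected number of pregnancies.**
- Women: 350 × 0.70 = 245.
- In the trial: 245 × 0.01 × 46/52 = 2.17, about 2.2.
- Per arm: 2.17 / 5 = 0.43. With a Poisson count, the chance of at least one in a given arm is 1 - exp(-0.433) = 35%.

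**Step 3: expected shift of an arm mean.**
- 0.433 × 10/70 = 0.06 points; 0.433 × 20/70 = 0.12 points.
- Standard error of a dose-placebo difference: 7 × √(2/70) = 1.18 points.

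**Step 4: effect if pregnancies do occur in the 4.8 mg arm.** The arm mean moves by k × g/70 for k pregnancies. This was added to the top-dose mean in the same simulation.

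| Pregnancies k | g | Shift (points) | Average probability of success |
|---|---|---|---|
| 0 | – | 0 | 84.3% |
| 1 | 10 | 0.14 | 81.6% |
| 1 | 20 | 0.29 | 78.5% |
| 2 | 10 | 0.29 | 78.7% |
| 2 | 20 | 0.57 | 71.8% |

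One pregnancy costs 84.3 - 81.6 = 2.7 to 84.3 - 78.5 = 5.8 percentage points.

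**Step 5: which criterion is exposed.** In the unshifted runs the flat-curve test rejected in essentially every run and the responder criterion was met in more than 99%. The target-dose criterion was met in 82% to 90%, depending on shape, so the loss comes mainly through that rule. Even with a 0.57-point shift the top-dose difference is 9.43 points, or 9.43/1.18 = 8.0 standard errors, so the PoCC test is safe. One patient can change an arm's observed responder proportion by at most 1/70 = 1.4 percentage points.

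**Step 6: placebo arm.** The same 0.14 to 0.29 points would be added to the apparent effect of every dose.

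**Limits.** k × g/70 approximates what the MMRM would do and ignores the added variance. Part of g may be ordinary regain after stopping drug, which treatment policy properly counts.

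**The case against.** The best defence is that this is a declared estimand choice. Protocol 2.1.1 makes the comparison regardless of early discontinuation, and 3.3.4.1 lists pregnancy among the medical reasons for stopping. Surgery for obesity and permitted later obesity treatment fall under the same strategy. The trial makes no confirmatory claims (Protocol 7.1), and SAP 7.4.1 says that the Phase 3 dose will also rest on tolerability, safety and other information. Two contraceptive methods are required, so events should be rare.

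The rarity stands and sets the severity. The estimand argument stands only in part: surgery and other drugs change the obesity outcome itself, whereas pregnancy changes what the scale measures.

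Three stronger readings are tempting, and the documents do not support them:

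- *No analysis excludes these weights.* The continuous secondary endpoints and the on-treatment summaries drop weights more than 28 days after the last dose. SAP 6.6 also describes a hypothetical strategy that treats off-treatment weights as missing. SAP 6.4 and 7.4.2 are not in the public text, so supplementary handling there cannot be ruled out.
- *Loss of success can be read off Protocol Table 7.5: 1.* The slope between its -10.0 and -9.5 rows is (84.4 - 70.5)/0.5 = 27.8 percentage points per point. That would give 3.9 and 8.1 for shifts of 0.14 and 0.29. But those rows rescale the whole dose-response curve, while one patient moves one arm; simulation gives 2.7 and 5.8.
- *Weights can be cut at conception using data already collected.* No visible passage puts a conception date in the CRF. Protocol 5.2.6.2.3 reports pregnancy on a separate monitoring form.

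**Conclusion.** The gap is real and minor. As written, weights measured in pregnancy count as the Week 46 outcome of the randomised arm in the primary MMRM, in MCPMod and in the responder analyses. The visible text of SAP 7.4.1 has no exception.

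A reader might infer that the proof-of-concept conclusion is at risk. It is not. The expected distortion is about a tenth or less of the standard error of a dose-placebo difference (0.12/1.18 = 0.10). That bound rests on the 1% failure rate, which the protocol gives for consistent and correct contraceptive use, and on the assumed g. What is exposed is the target-dose rule, and only if a pregnancy happens to fall in an influential arm: a loss of about 3 to 6 percentage points for one pregnancy in the 4.8 mg arm with g of 10 to 20. A late conception or early loss would displace weight less. The case for acting is that the rule is cheap to set before unblinding and awkward to set afterwards.

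**What to change.** In Protocol 7.2.2 and SAP 6.6, 7.4.1 and 7.5.2, name pregnancy as a separate intercurrent event with a hypothetical strategy. Weights from the first positive pregnancy test onward are treated as missing in the primary MMRM and in the responder multiple imputation. Use the test date as the cut. It differs from the COVID-19 cut, which keeps data to 28 days after the last dose, so it needs its own wording.

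Keep collecting the weights for safety, and report the treatment-policy result with all data as a pre-specified sensitivity analysis.

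Cost: a few sentences, one derived flag and one extra model run. A few observed weights are not used, and those patients' Week 46 values then rest on the missing-at-random assumption. Any weights between conception and the first positive test stay in.
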